3.3 Randomisation and Blinding

All participants will be assigned to a treatment regimen according to a randomisation schedule generated by Pharmacy and/or a Richmond Pharmacology statistician. In each cohort of 15 participants, 12 will be randomised to noribogaine and 3 will be randomised to placebo.

With 4 cohorts and replacement allowance the participants randomisation numbering will be as follows:

- Cohort 1 from 1001 to 1015, replacement subjects from 1101 to 1115
- Cohort 2 from 2016 to 2030, replacement subjects from 2116 to 2130
- Cohort 3 from 3031 to 3045, replacement subjects from 3131 to 3145
- Cohort 4 from 4046 to 4060, replacement subjects from 4146 to 4160

The trial will take place in a double-blinded fashion whereby participants and trial site staff are blinded to the active or placebo treatment. The trial site staff and participants will, however, be aware of the dose level being used.

To maintain blinding, placebos will be used at equivalent timepoints to treatment and participants will receive the same number of capsules with the same appearance.

The pharmacy staff preparing the IMPs will not be blinded to treatment assignment. During the trial, the individual randomisation codes will be kept in the site's clinical trials pharmacy, accessible to the pharmacy personnel only. Upon completion of the trial, after the database lock and after the blind is revealed, the randomisation list will be filed in the Trial Master File.

Sponsor staff involved in clinical decision-making (such as those involved in Safety Review Committee (SRC) decisions) will be blinded to trial treatment. Sponsor staff performing PK analysis will be unblinded but will deliver blinded PK data and reports to the blinded Sponsor and Investigator teams.

3.4 Adaptive Design

The use of an adaptive design has been implemented in areas of this trial with limits specified in the trial protocol section 3.2.

4. STATISTICAL ANALYSES

4.1 General Notes for Statistical Analyses

In general, descriptive statistics for continuous variables will include number of non-missing values (n), arithmetic mean, standard deviation (SD), median, minimum, and maximum.

Categorical variables will be summarized using frequency counts and percentages.

For all tables, descriptive statistics for minimum and maximum will be presented with the same decimal digits as the original data, and with 1 more decimal place than the original data for mean and median; SD and SE will be reported with 2 more decimal places than the original data.

The analyses will be presented overall (where appropriate) and by the treatment groups.

All collected data will be presented in by-subject listings. Listings will be ordered by treatment group and subject number and will include all randomised subjects.

Unless otherwise stated, baseline will be defined as the last non-missing value prior to first administration of trial drug. Changes from baseline values will be calculated as the post-baseline assessment value minus the baseline value. Only observed values from scheduled time points will be used to create summary tables, i.e. repeated measurements are made at a time point, the first scheduled value will be used for summary analysis, unless otherwise stated in relevant section of this SAP.

Deviations from the planned analyses will be described in the final clinical study report.

The raw datasets will be converted to SDTM and ADaM formats prior to TFL generation. A submission package will be created, consisting of the SDTM/ADaM datasets, define.xml, annotated CRFs, Reviewer's Guide, and all associated programming scripts.

The TFLs will be generated using SAS version 9.4 or higher, and the pharmacokinetic (PK) parameters will be calculated using Phoenix WinNonlin version 8.4 or higher.

4.2 Interim Analysis

No interim analysis is planned for this trial.

4.3 Analysis Sets

The analysis of data will be based on different analysis sets according to the purpose of analysis (Table 2). Participant eligibility for each analysis set will be finalised before the DB hard lock. A participant who withdraws prior to the last planned observation in a trial period will be included in the analyses up to the time of discontinuation.

Table 2: Analysis set

Randomised	All randomised participants. Participants will be analysed according to the intervention to which they were randomised. This population will be used for participants' disposition, demographic characteristics, and baseline characteristic summaries.
Safety	All participants who receive at least 1 dose of IMP. Participants will be classified according to the IMP they received.
PK	All randomised participants who have received at least 1 dose of IMP and have at least 1 evaluable PK parameter.
PD	All randomised participants who receive IMP, that have at least one valid pre-dose ECG assessment and one valid post-dose assessment. An ECG assessment will be considered valid if it is based on at least two evaluable replicates with measurable QT and RR. The analysis set for intensive cardiac assessment will be based on the intersection of the PK set and the ECG set. In addition, participants on placebo will be included with plasma concentrations of IMP set to 0. Individual QTc/concentration pairs will be excluded from this set if the time of ECG and the time of blood sampling are too far apart. Should a participant have no pair of PK and ECG measurements at the same timepoint satisfying this criterion, this participant will be excluded from the set.

Details of ECG/PK allowable time windows extracted from the data handling protocol (DHP) are presented in Appendix 1.

4.4 Subject Disposition

All subjects will be included in the summary of subject disposition. This will present the overall number of subjects, the frequency and percentage of subjects randomised and treated, and who completed or discontinued from the trial, along with reason for discontinuation.

Furthermore, the number and percentage of subjects in each analysis set will be tabulated. Discontinued subjects will be listed. Subject assignment to analysis sets will be listed. Screen Failures will not be listed or included in summary tables.

4.5 Demographic Characteristics

Individual participant demographics (age, gender, ethnicity and race) and body measurement data (height, weight, and BMI) will be listed. These demographic characteristics and body measurements will be summarised by treatment group and overall, using the safety analysis set.

Height will be measured in centimetres and weight in kilograms. BMI will be given in kg/m².

Other baseline characteristics such as alcohol breath test, smoking history, exercise test date-time will be listed only.

4.6 Inclusion and Exclusion Criteria

The inclusion and exclusion criteria text will be listed, as well as failed eligibility criteria for each randomised subject, if any.

4.7 Protocol Deviations

The final review of protocol deviations will be performed at the data review meeting prior to database lock. The protocol deviations will be listed.

4.8 Medical and Surgical History

Medical and Surgical history data will be coded using the Medical Dictionary for Regulatory Activities (MedDRA) dictionary Version 26.1 (or higher) and listed individually. Surgical history data will be listed separately. Medical and Surgical history data will be summarised using frequency and percentage by system organ class (SOC) and preferred term.

4.9 Trial Drug Administration

Trial drug administration data including treatment received, dose (unit), date and time of administration will be listed by subject.

4.10 Prior and Concomitant Medications

All prior and concomitant medications will be coded using the World Health Organization Drug Dictionary version 2024 (or higher) and will be listed individually using safety set. The frequency and percentage of prior and concomitant medications will be summarized by Anatomical Therapeutic Chemical and Preferred Name. Separate tables will be given for prior and concomitant medications.

Prior medications are defined as those for which the end date and time is prior to the date and time of first trial drug administration. Concomitant medications are defined as those with start date and time on or after the date and time of first trial drug administration and those with start date and time prior to the first trial drug

administration but with end date and time on or after the date and time of first trial drug administration.

If medication dates are incomplete and it is not clear whether the medication was concomitant, it will be assumed to be concomitant.

4.11 Safety Analysis

Safety analyses will be performed on the safety set, unless otherwise stated.

Safety analyses will include an analysis of all AEs, ECGs, clinical laboratory data, vital sign measurements and physical examination results and will be presented using descriptive statistics. No formal statistical analysis will be performed.

4.11.1 Adverse Events

A Treatment Emergent Adverse Event (TEAE) is defined as any adverse event which commences or any worsening of pre-existing conditions after the start of administration of trial drug. AEs with unknown start date/time will be assumed to be treatment-emergent unless the end date/time is known to be before the first administration of trial drug.

AE data will be listed and TEAEs summarised using descriptive statistics: the number (and percentage) of participants who experienced any adverse events (AE) and the number of AE episodes will be summarized for each treatment group. All AEs will be summarized and listed by using the SOC and Preferred Term assigned to the event using the MedDRA dictionary Version 26.1 (or higher). Furthermore, these events will be summarised by the maximum intensity. The number of participants who had drug-related AEs will also be summarised. Any serious adverse events (SAE) and/or AEs that led to withdrawal will be summarised and listed.

Subjects having multiple AEs within a category (e.g., overall, SOC and Preferred Term) will be counted once in that category. In each table, SOC and Preferred Term will be presented in descending order of overall incidence rate (alphabetical order will be used in case of equal rates).

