***Schedule of Assessments***

Trial visit	Screening	Admission	Treatment Period										Discharge or Early Termination	Follow-Up	
			-1	1	2	3	4	5	6	7	8	9	10		
Day	-37 to -3	-2	-1	1	2	3	4	5	6	7	8	9	10	11	15 (+/- 2 days)
Informed Consent a	X														
Eligibility (Inclusion/Exclusion Criteria)	X	X	X												
Demographics	X														
Medical History and Current Medications	X	X b													
Smoking History reporting	X														
Urine Drug Screen	X	X													X
Urine Cotinine Screen	X	X													X
HIV, Hepatitis B and C	X														
FSH Testing c	X														
β-HCG Testing d	X	X													X
Postural Assessment of Heart Rate and Blood Pressure n	X		X	X				X			X		X		
Exercise Stress Test	X														
Non-residential Visit	X														X
Check-in		X													
Study Residency		X	X	X	X	X	X	X	X	X	X	X	X	X	X
Check-out															X
Randomisation				X											
IMP Administration e				X	X	X	X	X	X	X	X	X			
Meals f		X	X	X	X	X	X	X	X	X	X	X	X	X	X

Trial visit	Screening	Admission	Treatment Period										Discharge or Early Termination	Follow-Up	
			-1	1	2	3	4	5	6	7	8	9			
Day	-37 to -3	-2	-1	1	2	3	4	5	6	7	8	9	10	11	15 (+/- 2 days)
Safety and Tolerability:															
AE Recording/ Concomitant Medications			→												
Vital Signs g	X	X	X	X	X	X	X	X	X	X	X	X	X	X	X
12-lead ECG Triplicate h	X	X	X	X	X	X	X	X	X	X	X	X	X	X	X
Holter	X														
Telemetry i			X	X	X	X	X	X	X	X	X				
Height, and BMI	X	X													
Body Weight	X	X													
Physical Examination	X	X												X	
Biochemistry/Coagulation/ Haematology	X	X		X j			X j							X	X
Urinalysis	X	X		X			X							X	
Serum Potassium, Magnesium & Calcium only j					X				X		X				
C-SSRS	X	X												X	
MEQ30				X k			X k				X k				
COVID Test	X	X	X	X	X	X	X	X	X	X	X	X	X	X	X
Pharmacokinetic Assessments:															
PK Blood Sampling l				X	X	X	X	X	X	X	X	X	X	X	X
PK Urine Sampling				X m							X m	X m	X m	X m	

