2.2 Endpoints

Primary

- Maximum plasma concentration (C_{max} : Day 1 & Day 8), time to maximum plasma concentration (T_{max} : Day 1 & Day 8), trough concentration prior to next dose (C_{12} , C_{24}), area under the curve at 12 hours and 24 hours (AUC_{0-12} hours, AUC_{0-24} hours: Day 1 & Day 8, and to infinity ($AUC_{0-\infty}$)), accumulation ratio for AUC, accumulation ratio C_{max} , terminal elimination rate constant (λ_z), half-life ($t_{1/2}$), clearance (CL/F) and volume of distribution (Vz/F), whole blood to plasma ratio (1 hour, 2 hours and 6 hours), amount excreted (Ae) (Day 1 & Day 8) and cumulative amount excreted (Cum Ae) (Day 1 & Day 8).
- QT interval corrected for heart rate using individual specific QT interval correction (QTcI) measures (Day 1 & Day 8). Concentration-QTc relationship assessed on placebo-adjusted change from baseline for QTcI ($\Delta\Delta QTcI$) (Day 1 and Day 8).

Secondary

- Adverse events will be elicited by a verbal probe (prior to any trial rating scales). Any events spontaneously reported by the participant or observed by Investigator's staff (physical examinations) will be recorded. Vital signs, clinical laboratory results and ECG abnormalities will be reported as an adverse event if considered clinically significant.

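### SAP 4.11.1 limits the any-event and episode counts to TEAEs but defines the SOC/Preferred Term and maximum-intensity tables on all AEs, so pre-dose events can enter those tables

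*SAP*

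**What the plan says.** SAP 4.11.1 defines a TEAE as "any adverse event which commences or any worsening of pre-existing conditions after the start of administration of trial drug". It then gives these rules in order:

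- The lead rule is "AE data will be listed and TEAEs summarised using descriptive statistics". A colon follows, and after it come the number and percentage of participants with any event and the number of episodes, by treatment group.
- The coded tables: "All AEs will be summarized and listed by using the SOC and Preferred Term assigned to the event".
- Intensity: "Furthermore, these events will be summarised by the maximum intensity".
- Relatedness: "The number of participants who had drug-related AEs will also be summarised". Serious events and events leading to withdrawal are also summarised and listed, again without the word TEAE.

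An event with unknown start is taken as treatment-emergent "unless the end date/time is known to be before the first administration of trial drug". A participant with several events in one category is counted once in that category.

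**The concern.** The section defines the treatment-emergent event, uses it for one rule, and then describes the coded tables on a wider set. The lead rule puts all AEs in listings and TEAEs in summaries. The coded-table rule puts all AEs in both. The two sets differ by the events that began before the first dose and did not worsen afterwards.

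Safety and tolerability is the trial's secondary objective, and the SOC/Preferred Term and maximum-intensity tables are where a reader looks for a dose pattern in particular events. A pre-dose event placed there appears as an event on noribogaine at a given dose, or on placebo. Two programmers could follow the same SAP and produce different tables. If the coded table carries an overall row, which the counting rule allows for, that row need not agree with the any-event count reported elsewhere.

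**Working it through.** The plan states no figure on this point, so there is none to reproduce. The check compares texts and then sizes one miscounted participant.

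**1. Event set for each output in SAP 4.11.1**

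| Output | Event set as worded | Open to pre-dose events? |
|---|---|---|
| Any-event and episode counts | TEAEs (content of the lead rule, after the colon) | No |
| SOC/Preferred Term | All AEs | Yes |
| Maximum intensity | Refers back to the coded-table sentence | Yes |
| Drug-related | AEs | Barely: a pre-dose event should not normally be judged drug-related |
| Leading to withdrawal | AEs | Barely: withdrawal before dosing puts the participant outside the safety set |

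**2. Is the limit supplied elsewhere?**

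- SAP 4.11 describes the scope of the safety analysis as all AEs.
- The safety set (SAP 4.3) requires at least one dose. It selects participants, not events by onset.
- The secondary endpoint (SAP 2.2) has no treatment-emergent limit: "Any events spontaneously reported by the participant or observed by Investigator's staff (physical examinations) will be recorded".
- SAP 4.10 separates prior from concomitant medications by the time of first dosing and gives each its own table. The AE section has no such split.

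So the limit is not supplied elsewhere.

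**3. Can pre-dose events be in the data?**

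- In the protocol's Schedule of Assessments, the arrow on the row "AE Recording/ Concomitant Medications" appears to begin before Day 1. The table as read is broken, so the exact start day is uncertain.
- Participants are admitted on Day -2, have telemetry and serial ECGs on Day -1, and are randomised on Day 1. Clinically significant ECG, vital-sign and laboratory findings are reported as AEs.
- The unknown-start rule allows for an AE that ended before dosing.

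These show that pre-dose events are possible. They do not show how often they occur.

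**4. Size**

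Inputs from SAP 3.1: 12 noribogaine and 3 placebo participants per cohort, four cohorts. Pooled placebo would be 4 × 3 = 12. Pooling is stated for the ECG summaries (SAP 4.12.1) but not for AEs, so both placebo denominators are shown.

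Shift in a term's incidence = 100 × k/n, where k is the number of participants whose only event under that term was pre-dose:

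| Group | n | k = 1 | k = 2 |
|---|---|---|---|
| Noribogaine dose group | 12 | 8.3 points | 16.7 points |
| Placebo, pooled | 12 | 8.3 points | 16.7 points |
| Placebo, one cohort | 3 | 33.3 points | 66.7 points |

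A participant who also has a TEAE under the same term changes nothing in the incidence row, because of the count-once rule. In the maximum-intensity table, that participant could still move to a higher category if the pre-dose event was the more intense.

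For the chance that a group is touched at all, let p be the share of participants with a pre-dose event under a term for which they have no TEAE. The documents give no value, so p is an assumption. With independent participants, P(at least one) = 1 − (1 − p)^n:

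| Assumed p | n = 12 | n = 3 |
|---|---|---|
| 2% | 1 − 0.98^12 = 21.5% | 5.9% |
| 5% | 1 − 0.95^12 = 46.0% | 14.3% |
| 10% | 1 − 0.90^12 = 71.8% | 27.1% |

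**The case against.** The strongest reply is that the intention is plain. A TEAE definition and a rule for unknown start dates serve little purpose unless the summaries are limited to TEAEs, and the coded-table sentence can be taken as a coding statement in which AE is shorthand after the lead rule. This is a fair guess at intent, but the text does not secure it. The same sentence covers listing as well as summarising. If AE there meant TEAE, the listings would be cut to TEAEs too, against the lead rule that AE data are listed.

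Several other objections stand in full:

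- The colon ties the any-event and episode counts to TEAEs. A reader might infer that the headline AE rate is inflated; the documents do not support that.
- The drug-related and withdrawal tables are barely exposed, for the reasons in the table above.
- A reader might infer that pre-dose AEs are to be expected. An imputation rule is a contingency, and residence with monitoring shows observation, not events.
- A reader might infer that every group's rates rise. A group with no such participant has unchanged incidence, and pre-dose events would be spread over many terms.
- No formal test is planned for safety, and every AE remains visible in the by-subject listings, so a miscounted event could be traced.

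**Conclusion.** The conflict is real but confined to the SOC/Preferred Term and maximum-intensity tables. There the stated rule, followed literally, counts events that began before first dosing and did not worsen. Each participant whose only event under a term was pre-dose shifts that term by 8.3 points in a noribogaine group, and by 8.3 or 33.3 points in placebo depending on pooling. How many such participants there would be is unknown; the 2% to 10% range is assumed and serves only to show that a group of 12 could readily be affected.

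A reader might go further and treat this as a threat to the secondary endpoint as such. The documents do not support that: the endpoint is defined as recorded adverse events rather than as a rate, and its analysis is descriptive, so no test or error rate changes. What remains is an ambiguity in tables that summarise the secondary objective. It is worth removing before they are programmed.

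**What to change.** In SAP 4.11.1, state that all AE summary tables, in particular those by SOC and Preferred Term and by maximum intensity, include TEAEs only. Add that AEs with onset before first dosing and no later worsening appear in listings only. Using TEAE in the drug-related and withdrawal sentences as well would keep the section uniform, although little depends on it there.

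The cost is a few words in the SAP and the same population label on the table shells. If the tables are already programmed, they need a treatment-emergent filter and a rerun. No data are lost, because pre-dose events stay in the listings, and the change only carries through the rule that the section states first.

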4.11.2 Laboratory Data

All safety clinical laboratory data, including potassium, magnesium & calcium, will be listed. Laboratory test results will also be compared to laboratory reference ranges and those values outside of the applicable range will be flagged as high (H) or low (L) and as being clinically relevant or not: the number of participants presenting out-of-range and clinically relevant values will be summarised. The quantitative laboratory data, along with changes from baseline will be summarised using descriptive statistics.

The qualitative urinalysis data, urine drug screen, serology and COVID test data will be listed only.

For summary statistics, a lab value with "<" will be replaced with a numeric value by removing the "<" sign. In the listings, the values will be displayed as originally reported by the laboratory.

4.11.3 Vital Signs

Vital signs data (supine SBP, DBP, HR, postural HR, tympanic temperature, oxygen saturation, respiratory rate) will be listed and summarised, along with changes from baseline, using descriptive statistics. Out-of-reference-range values will be flagged as high (H) or low (L) and as being clinically relevant or not by sub-investigators. The number of participants presenting out-of-range and clinically relevant values will be summarised.

Normal ranges for the relevant parameters are presented in Table 3 below.

Table 3: Vital Signs Normal ranges

Parameter	Normal Range
Temperature	35-38°C
Systolic Blood Pressure (Supine)	90-140 mmHg
Diastolic Blood Pressure (Supine)	55-90mmHg
Heart Rate (supine)	55-90 bpm
Postural change in Heart Rate	≤30 bpm
Respiration Rate	8-20 breaths per minute
Oxygen Saturation	93 - 100%

Vital signs performed pre and post exercise Tolerance Test (ETT) will be included within the listings and summary tables with timepoints names as Pre-EST and Post-EST.

4.11.4 Physical Examination

The physical examination will be performed during the trial will be listed only and include an assessment of the following: general appearance, skin, eyes, ears, nose, neck, lymph nodes, throat, heart, lungs, abdomen, musculoskeletal system, neurological system, and extremities.

- Absolute QTc interval prolongation
 - QTc interval > 450 ms
 - QTc interval > 480 ms
 - QTc interval > 500 ms
- Change from baseline in QTc interval
 - QTc interval increases from baseline > 30 ms
 - QTc interval increases from baseline > 60 ms
- Fulfilling both, absolute QTc values >480 ms and QTc >30 ms;

Additional categorical analysis will be presented as follows:

- Absolute PR values >200 ms, >220 ms, with a pre-dose value below the respective threshold
- $\Delta PR \geq 25\%$, i.e., post-dose PR outside the range of (0.75, 1.25) of the baseline value
- Absolute QRS duration >110 ms and >120 ms, with a pre-dose value below the respective threshold
- $\Delta QRS \geq 25\%$, i.e., post-dose QRS outside the range of (0.75, 1.25) of the baseline value
- Absolute HR of <50 bpm or ≥ 100 bpm, with a pre-dose value below the respective threshold
- Heart rate decrease $\geq 25\%$ from baseline to a HR of <50 bpm and/or increase $\geq 25\%$ from baseline to a HR of ≥ 100 bpm.

Figures

Mean values by treatment group (with placebo pooled across cohorts) and timepoint will be presented graphically for quantitative ECG parameters and their change from baseline. In addition, mean differences to placebo will also be given. Two-sided 90% confidence intervals will be shown for each treatment and timepoint.

